The original target sample size was 544, but UMN IRB approval was granted in May 22, 2018 to increase the sample size to 589 in case attrition was higher than expected. However, due to COVID-19, we completed enrollment in March 2020 with 504 participants and will not be enrolling more participants.

1. The first group (Sample A), consists of a cohort followed over one year. Recruitment of Sample A is complete. A total of 317 were enrolled; at this time, 214 have completed pre/post measures including the primary outcome, and a small number of participants continue to be followed. The remainder are lost-to follow up or did not complete primary outcomes measures. We will be adequately powered with 176 participants completing pre/post primary outcome measures.
2. The second group (Sample B), consists of a cross-sectional sample with no identifiable data collected for the study, to collect a secondary outcome measure. Recruitment of Sample B stopped early due to COVID-19. We collected data 272 clients at 16 sites at pre-assessment (17 per site) 187 clients at 11 sites at post-assessment. However, post-assessment data could not be completed at the final 5 sites after March 2020 for two reasons: 1) Food pantries in Minnesota stopped offering client choice shopping for food at the start of the COVID-19 pandemic, thus we could not assess what foods clients selected at their visit (the primary purpose of the measure), and 2) UMN's "sunrise plan" for human subjects research studies has so far not included community-based studies without a clear clinical treatment benefit for participants, due to the unpredictability of community environments. As it is unclear when these conditions necessary for data collection will change during the study period, we are proceeding with the study analysis without these data. As participants are not followed over time, there is no consideration of attrition.

Justification of Sample Size: [For qualitative and pilot studies, describe how the proposed sample size is appropriate for achieving the anticipated results. For quantitative studies, provide a power analysis that includes effect size, power and level of significance with references for how the sample size was determined. Explain the rate of attrition and possible number who fail the screening, with references as appropriate.]

Power Analysis:

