Healthy Eating Index (HEI). For the outcome of change in overall diet HEI scores (the primary outcome), power is computed based on the t-test at the individual client level, but sample size is inflated for the group randomization design by a factor of $1+(m-1)*ICC$ where m is the average cluster size and ICC is the intracluster correlation. A SD of 14.4 is based on change in individual total diet HEI scores from the PI's pilot study of 43 food shelf clients²¹ assuming that individual total diet variability is a better reflection of the variability in client selection than the variability across food

pantries. We anticipate an ICC for HEI scores of 0.05 based on the same data.²¹ Under these assumptions and using a two-sided type I error rate of 5%, this study would have 80% power to detect a mean difference in 7.5 HEI points between intervention and control. With a originally planned average cluster size m of 11 and number of clusters k of 16, we require at least 176 participants with pre/post measures, or at least 272 enrolled to account for 30% attrition. We have surpassed this number for our primary outcome. This calculation also yields more than adequate power to detect the same mean difference in the HEI of food selected at the visit based on actual the standard deviation in our baseline sample (secondary outcome), for which we collected two repeated-sectional samples (with the second sample of 187 collected at post-assessment),.

Enrollment of UConn Students and/or Employees: [Will UConn students be enrolled? If so, describe if these students include those who any key research personnel teaches, or for whom any key research personnel has responsibility. Will UConn employees be enrolled? If so, describe if these employees report to any key personnel. For each group, explain why this population is *necessary* to the study. Tip: convenience is not sufficient justification.]

N/A

Enrollment of Key Personnel, Spouses or Dependents/Relatives: Will study key personnel, spouses of key personnel, or dependents/relatives of any key personnel be enrolled in the study? If so, describe and provide justification.

[figure not shown]
N/A

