Design Overview: The intervention is an environmental-level intervention at 16 food pantries. Participants are exposed to the intervention through their normal pattern of visits to the food pantry (determined by the participant). It is a group-randomized study in which 8 pantries are randomly assigned to the intervention (“transformation”) and 8 are randomly assigned to the control (“delayed transformation”) arm. The intervention will be implemented over one year and will occur in two waves (4 intervention and 4 control food pantries in year 2, 4 intervention and 4 control food pantries in year 3). Clients will be recruited from intervention and control food pantries, and measures will be conducted before and after the intervention. The final period of the study focuses on dissemination of our findings.

Food pantry intervention (“transformation”) activities: At the food pantry level, activities support the goal of increasing the nutritional quality of foods available to clients to make the healthy choice

the easy choice. Food pantries will receive ongoing visits from trained UMN Extension educators, supervised by the study's Community Outreach Coordinator, who work with food pantry managers to increase the supply of healthy food through sourcing and the appeal and the appeal of healthy food through behavioral economics. This occurs over a period of months. Food pantries "transform into a SuperShelf" according to the 6 steps outlined below.

Pantries were selected via a request for applications to food pantries in the state of Minnesota. Food pantries will apply either via paper or online by responding to a brief list of questions to evaluate capacity to complete intervention and evaluation activities.

More information is available at www.SuperShelfmn.org

Control sites. Control food pantries ("delayed transformation sites") do not receive any intervention until completion of the evaluation. After evaluation measures are complete, they receive support from UMN Extension and the study Community Outreach Coordinator in transforming to be a SuperShelf.

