Primary outcome (HEI). To examine change in overall diet, we will use mixed-model linear regression models with fixed effects for treatment group, baseline client- and food pantry-level covariates, and a random effect for food pantry (to account for correlation within food pantries) to assess intervention effect on mean change. Change will be calculated as post-intervention score minus pre-intervention score in client-level overall diet HEI score. We will specify a correlation structure for the random effect appropriate for longitudinal data (e.g. autoregressive, Toeplitz or compound

symmetry). Pre and post-intervention component scores and change scores will be calculated for the HEI subcomponents for descriptive purposes. We will also proceed with a sensitivity analysis of the 11 sites where data was collected pre-COVID, as dietary habits may be different during COVID-19, for which we are powered to detect an effect size of 8.15 points.

Secondary and exploratory outcomes. For food selected at the visit, we will compare post intervention HEI scores between intervention and control groups, adjusted for clustering within the food pantry (random effects) and adjusted for food pantry-level baseline HEI bag check scores and relevant covariates (client and food pantry level). HEI subcomponent scores will be calculated for descriptive purposes. We will proceed with analysis of HEI bag check scores for the 11 sites in which we have complete pre/post data, for which we are powered to detect an effect size of 7.27 points. Change in CV health scores (Life's Simple 7) and satisfaction scores will be analyzed using models described above.

Inclusion/Exclusion Criteria: [List ALL inclusion and exclusion criteria. Any proposed exclusion criterion based on gender (women of childbearing potential), age, or race must include justification for the exclusion.]

Inclusion Criteria: Any adult who comes to a participating food pantry on a day in which data collection is taking place will be able to participate in the study, as long as they do not fit our exclusion criteria. This group, based on the demographic of adults who participate in food pantries' services will include groups with socioeconomic disadvantage. Only one adult per household may participate. We will enroll clients who speak English, Spanish or Somali. Participants must have access to a phone.

Exclusion Criteria:

- Under the age of 18
- Mentally incapable of providing informed consent

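### The stated 80% power for 7.5 HEI points at 176 completers uses client-level degrees of freedom; on the 14 between-pantry degrees of freedom it is about 75%

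*Combined protocol and SAP*

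**What the plan says.** The Power Analysis for the primary outcome, under Justification of Sample Size, describes its method openly: "power is computed based on the t-test at the individual client level, but sample size is inflated for the group randomization design". The inflation factor is 1 + (m − 1) × ICC, "where m is the average cluster size and ICC is the intracluster correlation". The inputs are an ICC of 0.05, a two-sided 5% test, m = 11 and k = 16. On variability, "A SD of 14.4 is based on change in individual total diet HEI scores". From these the section concludes that "this study would have 80% power to detect a mean difference in 7.5 HEI points between intervention and control", which requires 176 clients with pre and post measures, and it adds that this number has been passed.

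The section on numbers of participants repeats the benchmark for Sample A: "We will be adequately powered with 176 participants completing pre/post primary outcome measures". It also reports that "214 have completed pre/post measures including the primary outcome, and a small number of participants continue to be followed".

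On design, the Design Overview states: "It is a group-randomized study in which 8 pantries are randomly assigned to the intervention", with the other 8 as controls. The Data Analysis Plan for the primary outcome specifies a linear mixed model with "a random effect for food pantry (to account for correlation within food pantries) to assess intervention effect on mean change". It names no reference distribution or degrees-of-freedom method for the treatment effect.

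**The concern.** Clustering affects a group-randomised comparison in two ways. It enlarges the variance of the treatment effect, and it limits how well that variance can be estimated, because only 16 independent units were randomised. The design effect handles the first. The second enters through the degrees of freedom, and the Power Analysis says nothing about it. With 8 pantries per arm the difference is not negligible: the two-sided 5% critical value of t is 2.145 on 14 degrees of freedom and 1.974 on 174.

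The plan relies on the figure of 176 twice to say that the primary outcome is adequately powered. If that number does not deliver 80%, the margin that 214 completers appear to give is also overstated, and a reader interpreting a null result would credit the trial with more sensitivity than it has.

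**Working it through.** **Inputs.** SD of change 14.4, ICC 0.05, m = 11, k = 16, difference 7.5 points, two-sided 5% (all from the Power Analysis); 8 v 8 pantries (Design Overview); 214 completers to date (section on numbers of participants).

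**Formulas.** With N completers spread equally over 16 pantries:
- Design effect: DE = 1 + (N/16 − 1) × 0.05
- Standard error of the difference: SE = 14.4 × √(4 × DE / N)
- Power from the noncentral t distribution with noncentrality 7.5 / SE. The detectable difference is the value at which power is 80%.

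**Step 1: reproduce the plan.** N = 176: DE = 1 + 10 × 0.05 = 1.5; SE = 14.4 × √(6/176) = 2.659; noncentrality 7.5 / 2.659 = 2.821. On 174 degrees of freedom, power is 80.1% and the detectable difference 7.49. From the sample-size side, the normal formula gives 58 per arm, and 58 × 2 × 1.5 = 174, which is 15.8 clusters of 11 and rounds up to 16 × 11 = 176. The plan's figures are recovered, so there is no doubt how they were obtained.

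**Step 2: change only the degrees of freedom.** Same SE, 16 − 2 = 14 degrees of freedom:

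| Completers | DE | SE | df | Power for 7.5 | Detectable difference |
|---|---|---|---|---|---|
| 176 | 1.500 | 2.659 | 174 | 80.1% | 7.49 |
| 176 | 1.500 | 2.659 | 14 | 74.7% | 8.01 |
| 214 | 1.619 | 2.505 | 212 | 84.6% | 7.05 |
| 214 | 1.619 | 2.505 | 14 | 79.5% | 7.55 |
| 224 | 1.650 | 2.472 | 14 | 80.5% | 7.45 |

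On 14 degrees of freedom power reaches 80% at about 219 completers, or 224 if every pantry supplies a whole 14.

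**Step 3: unequal pantry sizes.** The documents give no completer counts by pantry. As an assumption, take a coefficient of variation (CV) of pantry size between 0.2 and 0.4, with DE = 1 + ((1 + CV²) × m − 1) × 0.05 and m = 214/16 = 13.375. At 214 completers on 14 degrees of freedom:
- CV 0.2: power 78.9%, detectable difference 7.61
- CV 0.3: 78.1%, 7.69
- CV 0.4: 76.9%, 7.79

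**Step 4: covariates.** Covariates that explain outcome variance raise power. On 14 degrees of freedom the variance cut needed to restore 80% is 1 − (7.5/8.012)² = 12.4% at 176, and 1 − (7.5/7.548)² = 1.3% at 214. Pantry-level covariates also use up degrees of freedom: on 12, power at 176 is 73.6%. The documents do not say how much variance the covariates explain, so the net effect is unknown.

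**Step 5: does the reference distribution matter at analysis?** In a null simulation of a random-intercept model (16 pantries of 13, ICC 0.05, 400,000 trials), the rejection rate was 6.4% with a normal reference, 6.3% with t on 206 degrees of freedom and 4.4% with t on 14. The plan does not say it will use a normal reference, so this shows only why the choice should be stated.

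**The case against.** The strongest reply is that the plan's sums are right for the method it discloses, and that the omission is a common approximation, not a slip in calculation. That is fair as a description, but the 80% is still presented as a property of this design, and with 16 pantries the approximation is about 5 percentage points too high.

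A second reply is that little now depends on it. Enrolment is closed, 214 completers are in hand with a few still in follow-up, and about five more would reach 80% if pantries are equal. At 176 the loss is about half an HEI point in detectable difference, small beside the uncertainty of an SD and ICC from a pilot of 43 clients. This largely stands: it limits the consequence but does not rescue the statement about 176.

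A third reply is that 14 degrees of freedom is a reasonable choice but not one the plan makes, and that t on 14 is slightly conservative for the planned model (4.4% type I error in the simulation). A separate simulation, with the mixed-model test calibrated to exactly 5% using the planning ICC, gave about 76.4% power at 11 per pantry and 80.2% at 13 per pantry. That calibration needs the true ICC, so it is an upper bound and not an available test. A Satterthwaite-type rule gave 74.6% and 78.8%, close to the figures above. So 219 and 224 should be read as approximate, but even the upper bound leaves 176 short of 80%.

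Finally, 214 is an interim count, so any power quoted for it should be updated when follow-up ends.

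**Conclusion.** The concern holds. On the plan's own inputs, 176 completers give about 75% power for 7.5 points, not 80%, and the difference detectable with 80% power is about 8.0. The whole gap comes from the degrees of freedom, since nothing else was changed between the two calculations. It is a misstated benchmark and not a materially smaller trial: 214 completers nearly restore the stated power, at about 79.5%. They do not provide the surplus that the plan's method implies (84.6%).

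These figures rest on the planning SD and ICC and on no credit for covariates; those for 214 and above also assume equal numbers per pantry. Unequal sizes would lower power at 214 to between 78.9% and 76.9% over the assumed range. Covariates could move it either way. The absence of a stated degrees-of-freedom method in the Data Analysis Plan is not itself a demonstrated error, but it is worth settling with only 16 pantries.

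**What to change.** - **Power Analysis:** state that, tested on about 14 between-pantry degrees of freedom, 176 completers give about 75% power for 7.5 points (detectable difference about 8.0); that about 219 are needed for 80% (224 at 14 per pantry); and that 214 give about 79.5% (detectable difference about 7.55). Say that these assume equal pantry sizes and no covariate adjustment, and update the last figure to the final count.
- **Section on numbers of participants:** replace the statement that 176 is adequate with the power at 176 and at the number actually completed.
- **Data Analysis Plan, primary outcome:** state that the treatment effect will be tested with between-pantry degrees of freedom, for example by Kenward-Roger or Satterthwaite.
- **Reporting:** give completers per pantry, so that the equal-size assumption can be checked.

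The cost is wording only, with no extra enrolment. The stated figures become slightly less favourable.

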For EACH Participant Population Describe Screening Procedures, if applicable: [Describe when participants will be screened and how this will occur. Include copies of all screening forms and related documents. Describe procedures to notify participants of the screening result, if applicable. Provide a copy of the screening instrument.]

. No screening of additional participants will take place.

Anticipated Study Time Frame: [Describe the estimated time frame of the study from anticipated start to anticipated finish. If the study will occur in more than phase include these in the time frame. Use of a table is often helpful.]

The total study period is five years (April 2017 to March 2022). Participants in Sample A, which assesses the primary outcome, are followed up with after 1 year. Study participants were enrolled from Jan 2018 to March 2020. Below is a visual representation of the originally planned study and its timeline. The intervention and evaluation occur in two waves (4 intervention and 4 control food pantries in year 2, 4 intervention and 4 control food pantries in year 3).

Design, Procedures, Materials and Methods: [Describe the study design, including the sequence of study procedures. Experimental procedures should be clearly described and labeled as such. If the study uses control or experimental groups, or different treatment arms, clearly describe what participation will be like for each of the groups or study arms. Tip: describe procedures in the order conducted, where they will be conducted and how long they will take to complete. The IRB strongly suggests that investigators incorporate *flexibility* into the study design to accommodate anticipated events (i.e. explain how missed study appointments can be made up by participants). If this study offers treatment for the participants' condition, complete the Treatment Study Supplemental Form (IRB-1C) and attach it to this application for review. Use of a table is often helpful here.]

[figure not shown]

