1. Take the Post survey online, over the phone, or by mail (\$15)
2. Complete two 24 hour diet recalls. (\$15 per recall)

Follow-up with Sample A: Participants can take the survey online via a REDCap link, over the phone with a data collector, or by mail. At follow up, participants are mailed a notification that we will be contacting them soon. Data collectors follow up by calling participants. When participants cannot be reached by phone, participants are emailed the survey by REDCap and mailed a hard copy of the survey. We also send a text reminder. Due to the transient nature of the study population, we will use a broad range of strategies to re-engage with participants at the time of follow-up. In particular, if it is determined that the phone number originally provided by the participant are not valid (e.g. incorrect number, disconnected service, etc.) we will employ the other methods for reconnecting with the participant, not exceeding 3 points of contact with these methods. Potential methods include: social media (e.g. SuperShelf's FaceBook page), WhitePages, and web-based phone/messaging services (e.g. WhatsApp, Viber) and LexisNexis. In our work with food pantry clients to date, we have found that many participants are interested in continuing to participate at follow-up, but delay completing activities due to the many competing priorities in their daily lives. For the final month of retention data collection in each Wave, participants will be given a "last chance" to participate, with an extra \$10 offered for completing the follow-up survey. This was successful in increasing follow-up during Wave 1.

Sample A survey procedures: Once participants have been contacted, they complete a survey that takes approximately 20 minutes. This can be completed on the phone with data collectors, though an online link, or by mail. No participants in Sample A completed the survey in Somali; therefore, follow-up will be done using English and Spanish surveys only. Upon completion of the survey, they are contacted by the Nutrition Coordinating Center at the University of Minnesota to complete two dietary recalls.

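### Pantries are allocated 4:4 by arm within two waves, but the primary HEI model does not commit to a wave term; precision is forgone if waves differ, without bias.

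*Combined protocol and SAP*

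**What the plan says.** All references are to the combined protocol and SAP.

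- **Allocation.** The Design Overview says that implementation "will occur in two waves (4 intervention and 4 control food pantries in year 2", with the same 4 and 4 in year 3. Anticipated Study Time Frame repeats this: "The intervention and evaluation occur in two waves (4 intervention and 4 control food pantries in year 2".
- **Primary model.** The Data Analysis Plan, under Primary outcome (HEI), specifies "mixed-model linear regression models with fixed effects for treatment group, baseline client- and food pantry-level covariates, and a random effect for food pantry". The covariates are not listed, and wave is not mentioned anywhere in the analysis plan.
- **Other outcomes.** Change in Life's Simple 7 "and satisfaction scores will be analyzed using models described above", so these outcomes inherit the same form.
- **COVID-19.** The plan adds: "We will also proceed with a sensitivity analysis of the 11 sites where data was collected pre-COVID", giving as its reason "as dietary habits may be different during COVID-19, for which we are powered to detect an effect size of 8.15 points". The arm and wave of those 11 sites are not given.
- **Planning ICC.** Under Power Analysis: "We anticipate an ICC for HEI scores of 0.05 based on the same data", the data being a pilot of 43 clients. The text does not say whether the 0.05 allows for differences between waves.
- **Timing.** Follow-up with Sample A refers to the first wave in the past tense: "This was successful in increasing follow-up during Wave 1".

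**The concern.** Wave is a grouping built into the allocation, and the arms are balanced within it. The usual practice is to analyse by the groups within which units were allocated. If mean HEI change differs between waves and the model ignores this, the wave difference goes into the between-pantry variance. With only 16 pantries that variance sets the standard error of the treatment effect.

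The plan itself gives a reason to expect such a difference. It allows that diets may have changed during COVID-19. Since first-wave follow-up is described as past, follow-up during the pandemic probably falls mainly in wave 2; that is an inference, not a statement in the documents. At stake are the precision of the primary comparison and an analysis choice left open, because an unlisted set of covariates lets wave be included or left out after the data are seen.

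**Working it through.** **Inputs from the documents:** SD of change 14.4; ICC 0.05; target difference 7.5 points; two-sided 5%; planned 11 clients in each of 16 pantries; 214 completers so far, so 214/16 = 13.375 per pantry.

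**1. The plan's own figure.** Per arm before inflation: 2 × (1.960 + 0.842)² × 14.4² / 7.5² = 57.9, rounded up to 58. The design effect is 1 + (11 − 1) × 0.05 = 1.5, giving 87 per arm and 174 in total. The plan states 176 (11 × 16), for which normal-theory power is 80.5%. The figure reproduces.

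**2. Why there is no bias with 16 pantries.** Each arm has 4 pantries in each wave. A shift D common to wave 2 adds D/2 to both arm means and cancels in their difference. This takes completers per pantry as roughly equal.

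**3. Standard error.** Variance of a pantry mean: v = 14.4² × (0.05 + 0.95/13.375) = 25.10. True SE of the arm difference: √(v × (1/8 + 1/8)) = 2.50, whatever D is. Without wave, the root-mean-square estimated SE is √[(14v + 4D²)/14/4]:

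| D (points) | Estimated SE without wave | Ratio to 2.50 |
|---|---|---|
| 0 | 2.50 | 1.00 |
| 2 | 2.56 | 1.02 |
| 4 | 2.72 | 1.09 |
| 6 | 2.97 | 1.19 |

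**4. Power at 7.5 points.** Regression of pantry means on treatment (14 df) or on treatment plus wave (13 df), by simulation. With no shift, noncentral t gives 79.5% without wave and 79.0% with it. The shifts are assumed and are added to ICC 0.05. The second pair of columns lets 5 of the 8 wave 2 pantries, chosen at random, carry the shift. Five is the number of sites outside the 11-site set (16 − 11), all assumed to be in wave 2.

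| Shift | All 8 shift: without | with wave | 5 of 8 shift: without | with wave |
|---|---|---|---|---|
| 2 | 78.1% | 79.0% | 78.2% | 78.2% |
| 4 | 74.1% | 79.0% | 74.3% | 75.7% |
| 6 | 67.1% | 79.0% | 68.0% | 71.7% |

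When all 8 shift, type I error without wave is about 4.6%, 3.4% and 2.2%, and the two models break even at a shift of about 1.2 points. When 5 of 8 shift, a wave term cannot recover 79%, because affected and unaffected pantries still differ within wave 2. The squared true SE becomes v/4 + 15D²/448, so the SE is 2.53, 2.61 and 2.74 at shifts of 2, 4 and 6.

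**5. If the ICC of 0.05 already includes the wave difference.** Residual between-pantry variance is then 0.05 × 14.4² − D²/4 = 10.4, 9.4, 6.4 and 1.4 at D = 0, 2, 4 and 6. With all 8 pantries shifting equally, power without wave is about 80%, 80.5% and 82.5% at 2, 4 and 6 points, no lower than the 79.5% at no shift.

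**The case against.** **The plan already has room for wave.** It can be read as one of the pantry-level covariates, so a reader who infers that wave is excluded goes too far. What stands is that nothing commits the analyst to it.

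**Nothing planned is shown to be at risk.** A reader might infer that the trial will miss its 80% power. The documents do not support that. They give no wave difference, and power falls only if the shift comes on top of an ICC of 0.05. If the 0.05 includes it, power is no lower than at no shift. Below the break-even shift, adding wave slightly lowers power. This objection stands in full, so the loss is forgone precision.

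**A uniform COVID-19 shift across wave 2 is generous.** If some wave 2 sites finished before the pandemic, the gain from a wave term shrinks to about 0, 1.4 and 3.7 power points at 2, 4 and 6 points. This also stands, and both patterns are shown above.

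**The 11-site analysis.** A reader might infer that this sensitivity analysis is biased, since an odd number of sites cannot keep 4:4 in both waves. But the set is defined as the pre-COVID sites, and COVID-19 is the only cause of a wave difference that the documents suggest. No bias figure for that set is supported.

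**Stratification.** The documents give 4 and 4 per wave without saying in words that randomisation was stratified by wave. The balance argument needs only the counts.

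**Conclusion.** The point holds as a minor one. The 16-pantry HEI model does not commit to a factor on which the arms are balanced by design. Leaving it out does not bias the estimate or invalidate the test. If waves differ, the test becomes conservative and some precision is lost. Under the assumed shifts of 2 to 6 points on top of ICC 0.05, a wave term gains about 1 to 12 power points if all wave 2 pantries shift alike, and about 0 to 4 if only 5 of 8 do. If waves do not differ, it costs about half a point.

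These figures rest on SD 14.4, ICC 0.05, equal pantry sizes of about 13.4 completers and a pantry-level t-test. The size of the shift and the pantries it affects are assumptions. For Life's Simple 7 and satisfaction the documents give no SD or ICC, so only the direction of the effect carries over.

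**What to change.** Name wave as a fixed effect in the 16-pantry primary HEI model, and in the Life's Simple 7 and satisfaction models that share its form. Record this before results by arm are seen. The planned sample size does not change. The cost is a line of text and one between-pantry degree of freedom (14 to 13), taking power from 79.5% to 79.0% if waves do not differ. A wave term does not correct for COVID-19 exposure that differs by arm within a wave, and is not proposed for that.

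As a reporting suggestion only: tabulate the 11 pre-COVID sites by arm and wave, so that readers can see what the sensitivity analysis compares.

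### Neither the power calculation nor the mixed-model analysis names pantry-level degrees of freedom, although arm varies only between 16 (or 11) pantries

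*Combined protocol and SAP*

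**What the plan says.** **Power Analysis (under Justification of Sample Size).** For the primary outcome, "power is computed based on the t-test at the individual client level", and "sample size is inflated for the group randomization design by a factor of" 1+(m-1)×ICC. The inputs are an SD ("A SD of 14.4 is based on change in individual total diet HEI scores"), an ICC ("We anticipate an ICC for HEI scores of 0.05 based on the same data"), a two-sided 5% error rate, m = 11 and k = 16. The conclusion is that "this study would have 80% power to detect a mean difference in 7.5 HEI points", with 176 completers. The section on numbers enrolled repeats that 176 completers are adequate and reports 214 so far.

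**Design Overview.** The pantry is the unit of randomisation, 8 per arm.

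**Data Analysis Plan, primary outcome.** A linear mixed model of client change scores has fixed effects for arm and for client- and pantry-level covariates, and "a random effect for food pantry (to account for correlation within food pantries"). The covariates are neither named nor counted. A sensitivity analysis uses the 11 sites measured before COVID-19, with a stated detectable effect of 8.15 points.

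**Data Analysis Plan, secondary outcomes.** "We will proceed with analysis of HEI bag check scores for the 11 sites in which we have complete pre/post data", with a stated detectable effect of 7.27 points. This model has a pantry random effect and adjusts for the pantry's baseline cart HEI.

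No section gives a degrees-of-freedom method, a reference distribution for the model's arm effect, or a small-sample correction.

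**The concern.** Every client of a pantry is in the same arm, so the arm effect is judged against variation between pantries. A design effect and a random intercept bring the standard error to about the right size. They do not allow for the fact that the pantry variance is itself estimated from 16 or 11 units. That uncertainty calls for a t reference on about k-2 df, less one for each pantry-level covariate, or a correction such as Kenward-Roger.

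Two things are at stake. First, the plan leaves open a choice that affects p-values and interval widths, and one option available to the analyst (z or client-level df) does not keep the stated 5% error rate. Second, the stated power and detectable effects take no account of pantry-level df, so they are more favourable than the design delivers.

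**Working it through.** **Inputs from the plan.** SD of change 14.4; ICC 0.05; difference 7.5; two-sided alpha 0.05; k = 16 (8 v 8); m = 11; 214 completers so far; 187 post-assessment carts at 11 sites (17 per site).

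**1. Reproduce the plan's sample size.**
- Per arm, ignoring clustering: 2 × (1.960 + 0.842)² × 14.4² / 7.5² = 57.9, so 58 (59 with a t-test).
- Design effect: 1 + (11 - 1) × 0.05 = 1.5.
- Total: 2 × 58 × 1.5 = 174 (177 with the t-test). The stated 176 is 16 × 11, so it reproduces, and it does so without pantry-level df.

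**2. Power on pantry-level df.**
- At N = 176: SE = 14.4 × √(2 × 1.5 / 88) = 2.659, and 7.5 / 2.659 = 2.821. Normal reference: Φ(2.821 - 1.960) = 80.5%. Noncentral t, 14 df, critical value 2.145: 74.6%. The difference detectable with 80% power moves from 7.45 to 8.01.
- At N = 214: m = 13.375, design effect 1.619, SE = 14.4 × √(2 × 1.619 / 107) = 2.505. Power is 79.5% on 14 df, and the detectable difference is 7.55.

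**3. The 11-site detectable effects.** The plan gives neither the completers at those sites nor the cart SD, so 8.15 and 7.27 cannot be reproduced from stated inputs. If they were computed with a normal reference, the implied SEs are 8.15 / 2.802 = 2.909 and 7.27 / 2.802 = 2.595. On pantry-level df they become about 9.2 (9 df) and 8.3 (8 df, one being spent on the baseline cart score).

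**4. Limits for a z-based test**, from P(|T| > 1.96) and the ratio of critical values:

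| df | Case | Critical t | Size with z | Correct interval wider by | z interval too narrow by |
|---|---|---|---|---|---|
| 14 | 16 pantries | 2.145 | 7.0% | 9.4% | 8.6% |
| 9 | 11 pantries | 2.262 | 8.2% | 15.4% | 13.4% |
| 8 | 11 pantries, one pantry-level covariate | 2.306 | 8.6% | 17.7% | 15.0% |

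**5. Size at the plan's ICC.** The limits in step 4 are reached only when the pantry variance is well above zero. At small ICC the variance estimate is often held at zero and the error is pooled, which reduces the inflation. Simulated size of a balanced random-intercept REML model with no pantry-level covariate, z reference:

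| ICC | 16 pantries, m = 11-13 | 11 pantries, m = 13-17 (6 v 5 assumed) |
|---|---|---|
| 0 | about 4% | about 4% |
| 0.01 | about 5% | about 5% |
| 0.05 | 6.2-6.4% | 6.8-7.2% |
| 0.10 | 6.8% | 7.7-7.9% |

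Client-level df (N-2) in place of z lower these by about 0.1-0.2 points; at ICC 0.05 with 16 pantries that gives 6.1-6.3%. One pantry-level covariate adds about 0.1 point at ICC 0.05. The simple between-pantry t reference (k-2 df) runs at about 4.3-4.4% with 16 pantries and about 4% with 11 at ICC 0.05.

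**The case against.** A reader might infer that the analysis ignores clustering, or that it tests arm at client level. The documents do not support that. The sample size is inflated for clustering, and the primary and cart models both carry a pantry random effect. The client-level t-test is named only as a sample-size device, and it cannot be read across to the mixed model.

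A reader might also infer that the primary test will run at 7-8%. That is not supported either. The plan is silent on the reference distribution; it does not choose z. An analyst who used between-pantry df would comply fully with the plan and see no inflation. At the anticipated ICC the primary figure is 6.0-6.5% even with z or client-level df, the 8% end belongs to 11-site analyses at a higher ICC, and near zero ICC the z test is slightly conservative.

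Finally, 214 completers exceed the 176 required, and at that number power on 14 df is 79.5%, practically the planned 80%. So it would be wrong to conclude that the primary comparison is now materially underpowered.

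All of this stands, and it limits the point. It does not remove it: the plan leaves the reference open with 16 and 11 clusters, and the claim of adequate power at 176 does not hold on pantry-level df.

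**Conclusion.** The point holds in a conditional and modest form. Clustering is handled; pantry-level degrees of freedom are not specified in the analysis and not used in the power calculation.

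- **Type I error, if z or client-level df are used:** about 6.0-6.5% for the primary outcome and about 7% for the 11-site analyses at ICC 0.05. With no pantry-level covariate, the limits are 7.0% and 8.2% as the ICC rises.
- **Intervals:** z-based ones are up to 8.6% (14 df) or 13.4% (9 df) too narrow.
- **Power:** 74.6% rather than 80% at 176 completers; 79.5% at 214.

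These figures assume equal cluster sizes, SD 14.4, ICC 0.05 unless stated otherwise, and a 6 v 5 arm split at 11 sites, which the documents do not give. The power figures use a t-test on k-2 df with no pantry-level covariate. Each such covariate costs about one more df, and their number is not stated. The gap does not invalidate the design, but it should be closed before the arm comparison is run.

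**What to change.** 1. State in the Data Analysis Plan that arm effects in the primary, 11-site sensitivity and cart models are tested, and intervals built, with REML and Kenward-Roger df, or else with a t reference on between-pantry df less the number of pantry-level covariates.
2. Name the pantry-level covariates in advance, so that the df are known.
3. Restate the power at 176 completers (74.6% on 14 df with no pantry-level covariate) and add the figure at 214. Restate the 8.15 and 7.27 point effects on pantry-level df, with the SD, ICC, cluster sizes and arm split behind them.

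**Cost.** A few sentences and a software option; no new data. Intervals become slightly wider and the stated power less favourable. The simple between-pantry df are somewhat conservative at ICC 0.05 (about 4.0-4.5%), which is a reason to list Kenward-Roger first.
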